### **3.3.2 Inclusion criteria**

Subjects will only be included into the trial, if they meet the following criteria:

1. Despite of moderate renal impairment (Group 1) healthy male or female subjects according to the assessment of the investigator, based on a complete medical history including a physical examination, vital signs (BP, PR), 12-lead ECG, and clinical laboratory tests
2. eGFR based on CKD-EPI formula for Group 1 between 30 and 59 mL/min/1.73m^2 and for Group 2  $\geq 90$  mL/min/1.73m^2
3. Age of 18 to 79 years (incl.)
4. BMI of 18.5 to 34 kg/m^2 (incl.)
5. Signed and dated written informed consent prior to admission to the study in accordance with GCP and local legislation
6. Male subjects, or female subjects who meet any of the following criteria (according to the CTFG Recommendations related to contraception and pregnancy testing in clinical trials, methods with a failure rate of less than 1% per year) starting from at least 30 days before the first administration of trial medication and until 30 days after trial completion, e.g.:
  - Use of adequate contraception, e.g. any of the following methods *plus* condom: implants, injectables, combined oral or vaginal contraceptives (inhibition of ovulation)
  - Hormonal intrauterine device
  - Sexually abstinent (defined as refraining from heterosexual intercourse during the entire period of risk)
  - A vasectomised sexual partner (provided that vasectomy was performed at least 1 year prior to enrolment and the vasectomised partner has received medical assessment of the surgical success)
  - Surgically sterilised (including bilateral tubal occlusion, hysterectomy)

Proprietary confidential information © 2018 Boehringer Ingelheim International GmbH or one or more of its affiliated companies

- Postmenopausal, defined as at least 1 year of spontaneous amenorrhea (in questionable cases a blood sample with simultaneous levels of FSH above 40 U/L and estradiol below 30 ng/L is confirmatory)

### 3.3.3 Exclusion criteria

Subjects who meet any of the following criteria will not enter into this trial:

Healthy subjects

1. Any finding in the medical examination (including BP, PR or ECG) is deviating from normal and judged as clinically relevant by the investigator
2. Repeated measurement of systolic blood pressure outside the range of 90 to 140 mmHg, diastolic blood pressure outside the range of 50 to 90 mmHg, or pulse rate outside the range of 50 to 90 bpm
3. Any laboratory value outside the reference range that the investigator considers to be of clinical relevance
4. Any evidence of a concomitant disease judged as clinically relevant by the investigator
5. Gastrointestinal, hepatic, renal, respiratory, cardiovascular, metabolic, immunological or hormonal disorders
6. eGFR calculated by CKD-EPI formula  $< 90 \text{ mL/min/1.73m}^2$

Subjects with moderate renal impairment

7. Subject with significant diseases other than moderate renal impairment.  
*A significant disease is defined as a disease which in the opinion of the investigator:*
  - puts the subjects at risk because of participation in the study
  - may influence the results of the study
  - may influence the subject's ability to participate in the study
  - is not in a stable condition*Diabetic or hypertensive subjects can be entered in this trial if the disease is not significant according to these criteria.*
8. Any finding of the medical examination (including BP, PR and ECG) of clinical relevance
9. Moderate and severe concurrent liver function impairment (e.g. due to hepatorenal syndrome) or biliary obstruction
10. Clinically relevant laboratory abnormalities (except for renal function tests or deviation of clinical laboratory values that are related to renal impairment)
11. eGFR calculated by CKD-EPI formula  $\geq 60 \text{ mL/min/1.73m}^2$  and  $< 30 \text{ mL/min/1.73m}^2$

For all subjects

12. Cholecystectomy and/or surgery of the gastrointestinal tract that could interfere with the pharmacokinetics of the trial medication (except appendectomy and simple hernia repair)
13. Diseases of the central nervous system (including but not limited to any kind of seizures or stroke), and other relevant neurological or psychiatric disorders
14. History of relevant orthostatic hypotension, fainting spells, or blackouts

Proprietary confidential information © 2018 Boehringer Ingelheim International GmbH or one or more of its affiliated companies

15. Chronic or relevant acute infections
16. History of relevant allergy or hypersensitivity (including allergy to the trial medication or its excipients)
17. Use of drugs within 30 days prior to administration of trial medication if that might reasonably influence the results of the trial (incl. QT/QTc interval prolongation)
18. Participation in another trial where an investigational drug has been administered within 30 days prior to planned administration of trial medication or longer if required by local regulation, or within 5-half-lives of the investigational agent taken (whichever is longer), or current participation in another trial involving administration of investigational drug
19. Smoker (more than 10 cigarettes or 3 cigars or 3 pipes per day)
20. Inability to refrain from smoking on specified trial days
21. Alcohol abuse (consumption of more than 20 g per day for females and 30 g per day for males)
22. Drug abuse or positive drug screening
23. Blood donation of more than 100 mL within 30 days prior to administration of trial medication or intended donation during the trial
24. Intention to perform excessive physical activities within one week prior to administration of trial medication or during the trial
25. Inability to comply with dietary regimen of trial site
26. A marked baseline prolongation of QT/QTc interval (such as QTc intervals that are repeatedly greater than 450 ms in males or repeatedly greater than 470 ms in females) or any other relevant ECG finding at screening
27. A history of additional risk factors for Torsades de Pointes (such as heart failure, hypokalemia, or family history of Long QT Syndrome)
28. Subject is assessed as unsuitable for inclusion by the investigator, for instance, because considered not able to understand and comply with study requirements, or has a condition that would not allow safe participation in the study

Female subjects will not be allowed to participate if any of the following applies:

29. Positive pregnancy test, pregnancy or plans to become pregnant within 30 days after study completion
30. Lactation period

Male subjects will not be allowed to participate if any of the following applies:

31. Male subjects with WOCBP partner who are unwilling to use male contraception (condom or sexual abstinence) from the first administration of trial medication until 30 days after last administration of trial medication

For study restrictions, refer to [Section 4.2.2](#).

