#### *Pharmacokinetics in healthy subjects*

Following both single and multiple doses of 10 and 15 mg, BI 1467335 Cmax and AUC0-24 increased in a more than dose proportional manner on Days 1, 14 and 28 ([Figure 1.2: 1](#)). Resulting from the accumulation of BI 1467335 following repeat oral dosing, quantifiable BI

Proprietary confidential information © 2018 Boehringer Ingelheim International GmbH or one or more of its affiliated companies

1467335 concentrations could be measured up to 4 h and 8 h postdose for 10 and 15 mg respectively on Day 1; and up to 24 h postdose on Days 14, and Day 28. Resulting from the limited time period over which quantifiable BI 1467335 concentrations could be measured on Day 1; the resulting  $AUC_{0-24}$  values on Day 1 need to be regarded with caution, as they may be underestimates, due to the large number of concentrations below the assays lower limit of quantification

The observed apparent elimination half-life (gMean) for BI 1467335 is significantly shorter on Day 1 (<1 h) compared to Days 14 and 28, (<4 h following 10 mg and < 9 h following 15 mg on Day 28). Despite the short apparent elimination half-lives, BI 1467335 significantly accumulates following q.d. dosing. For 10 mg q.d.,  $C_{max}$  increased by approximately 26-fold on Day 14 and 40-fold on Day 28, and  $AUC_{0-24}$  increased by approximately 58-fold on Day 14 and 159-fold on Day 28. For 15 mg q.d. dosing,  $C_{max}$  increased by approximately 14-fold on Day 14 and 16-fold on Day 28, and  $AUC_{0-24}$  increased by approximately 72-fold on Day 14 and 82-fold on Day 28.

Taking all the BI 1467335 data together, including trough concentrations, 1 h postdose samples along with  $AUC_{0-24}$  values, they suggest that steady state may be attained close to Day 14 following 15 mg q.d., whereas it was not attained by Day 14 following 10 mg q.d.. Following 10 mg q.d.,  $C_{max}$  and  $AUC_{0-24}$  are approximately 54% and 180% higher respectively on Day 28 compared to that on Day 14, whereas following 15 mg q.d.,  $C_{max}$  and  $AUC_{0-24}$  are approximately 13 and 15 % higher respectively on Day 28 compared to that on Day 14. For further details, please refer to the current 'Investigator's Brochure (IB)' [\[c04751792\]](#).

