Thus, BI 1467335 appears to display both dose and time dependent kinetics, where BI 1467335  $C_{max}$  and  $AUC_{0-24}$  values on Days 14 and 28 are greater than predicted from Day 1 data. BI 1467335 accumulation may in part be due to irreversible binding to AOC3 enzymes which are present in many different tissues within the body (Target Mediated Drug Disposition). This may explain the observation that steady state appears to be attained earlier following 15 versus 10 mg q.d. the highest dose tested to date.

[figure not shown]

Figure 1.2: 1

Geometric Mean BI 1467335 concentration-time profiles following single and multiple BI 1467335 dosing, 10 mg q.d. (left graph) and 15 mg q.d. (right graph), to healthy subjects on Days 1, 14 and 28 (up to 24 h postdose, semi-log scale)

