#### *Pharmacodynamics in healthy subjects*

AOC3 activities and their change from baseline were determined throughout study PXS-4728A-101 [[c09036683](#)]. During the SRD part of the study, a strong, dose related response to AOC3 activity inhibition could be demonstrated with increasing numbers of subjects achieving a reduction of 90% with increasing doses. At the highest single dose of 20 mg, AOC3 inhibition of greater than 90% was reported up to 12 hours post-dose in 5 of 6 subjects, with the mean SSAO inhibition at 24 hours being greater than 80%. The maximum inhibition was observed within 2 hours of single dose administration for most subjects across all dose groups.

During the MRD part of the study, inhibition of AOC3 activity at 24 hours post-dose on Day 14 remained greater than 90% for all subjects receiving a daily dose of 6 or 10 mg BI 1467335. At the lowest repeat dose level of 3 mg BI 1467335 per day, the AOC3 inhibition was greater than 80% at 24 hours post-dose on Day 14 in all subjects.

For further details, please refer to the current 'Investigator's Brochure (IB)' [[c04751792](#)].

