#### Drug-related risks and safety measures

Assessment of drug related risks is mainly based on data of an ongoing phase I study investigating safety, tolerability and pharmacokinetics of 10 mg, 15 mg and 20 mg q.d. of BI 1467335 for 28 days in healthy subjects. Data have been obtained for the complete 10 mg dose group (9 on active and 3 on placebo) and 7 subjects (5 on active and 2 on placebo) who completed the 15 mg q.d. treatment. The 20 mg q.d. dose group has recently completed treatment as well, however data evaluation is still ongoing. Regarding the 10 mg and 15 mg dose group and as already observed in a preceding 2 week study [[c09036683](#)] there were no SAEs and no AEs considered to be dose limiting. Nearly all of the AEs were of mild intensity. One subject assigned to 15 mg q.d. discontinued after receiving the 5th dose because of a common cold. There were no changes in safety labs, vital signs or ECGs readings considered to be clinically relevant. While the evaluation of the 20 mg dose group is ongoing there were no SAEs and no AEs considered being dose limiting as well. These findings are consistent with results of a preceding SRD/MRD study investigating a dose range of up to 10 mg of BI 1467335 administered for 14 days.

Following both single and multiple doses of 10 and 15 mg of BI 1467335  $C_{max}$  and  $AUC_{0-24}$  increased in a more than dose proportional manner on Days 1, 14 and 28 [[c04751792](#)]. Despite the short apparent elimination half-lives, BI 1467335 significantly accumulates following q.d. dosing. For 10 mg q.d.,  $C_{max}$  increased by approximately 26-fold on Day 14 and 40-fold on Day 28, and  $AUC_{0-24}$  increased by approximately 58-fold on Day 14 and 159-fold on Day 28. For 15 mg q.d. dosing,  $C_{max}$  increased by approximately 14-fold on Day 14 and 16-fold on Day 28, and  $AUC_{0-24}$  increased by approximately 72-fold on Day 14 and 82-fold on Day 28.

The exposure ratio ( $AUC_{0-24}$ ) between the 10 mg and 15 mg dose group is in a range of about 4.7 fold. This should provide a sufficient safety margin in renally impaired subjects receiving a dose of 10 mg q.d., taking into consideration that a 4.7 fold higher exposure was also well tolerated in healthy subjects.

Taken together no specific drug-related risks are anticipated. Still, the following safety measures will be applied in this study in order to minimize the risk for the participating subjects:

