The REP for BI 1467335, when measurable drug levels or PD effects are still likely to be present after the last administration, is not known for this clinical trial. Therefore, all AEs reported until the end of trial examination (last per protocol contact) will be considered on treatment (please see [Section 7.3.3](#)).

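### Criterion 18 lets a subject previously dosed with BI 1467335 enter after 30 days, and the documents do not show that 30 days restores a first-dose state for the Day-1 primary endpoints (minor)

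*Protocol*

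**What the plan says.** Protocol Section 3.3.3 deals with earlier drug use in two criteria for all subjects. Criterion 18 excludes "Participation in another trial where an investigational drug has been administered within 30 days prior to planned administration of trial medication", or longer if local regulation requires, or "within 5-half-lives of the investigational agent taken (whichever is longer"). Criterion 17 excludes "Use of drugs within 30 days prior to administration of trial medication if that might reasonably influence the results of the trial". Neither these nor any other criterion in Sections 3.3.2 and 3.3.3 mentions earlier treatment with BI 1467335 or, under its former name, PXS-4728A.

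Section 1.2 calls the compound an irreversible AOC3 inhibitor. It gives apparent half-lives of under 1 h on Day 1 and "<4 h following 10 mg and < 9 h following 15 mg on Day 28", notes marked accumulation despite them, and offers a partial explanation: "BI 1467335 accumulation may in part be due to irreversible binding to AOC3 enzymes". On the residual effect period, covering measurable drug or pharmacodynamic effect, Section 5.2.2.2 says that it "is not known for this clinical trial".

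Previously dosed people exist. Section 1.2 describes a 14-day and a 28-day study in healthy subjects, and Section 2.3 adds of the latter: "The 20 mg q.d. dose group has recently completed treatment as well".

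Day-1 AUC0-24 and Cmax are primary endpoints, alongside their Day-28 counterparts (Protocol 5.5.1.1, SAP 5.1).

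**The concern.** A washout counted in plasma half-lives suits a drug whose effect leaves with the drug. The protocol gives reasons to doubt that here. After a single 20 mg dose (HCl salt), inhibition was still substantial a day later, "with the mean SSAO inhibition at 24 hours being greater than 80" per cent, whereas first-dose plasma levels in the later study were quantifiable only to 4 h at 10 mg and 8 h at 15 mg.

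If part of the target were still occupied from an earlier trial, the protocol's tentative explanation implies a higher exposure after the next first dose. Because the earlier studies used healthy subjects, a pre-exposed entrant would most plausibly be a Group 2 control. That would pull the Day-1 impaired/normal ratio downwards, in a trial meant to support the inclusion of renally impaired patients in later studies.

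Nothing in the plan would reliably reveal this. The Day-1 pre-dose plasma and urine blanks (Section 6.1) can show residual drug but not occupied enzyme. AOC3 activity is not measured (Section 5.6 is marked not applicable). A pre-exposed subject would breach no entry criterion, so no deviation category in SAP Table 6.2: 1 clearly applies. The SAP has no sensitivity analysis for prior exposure.

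**Working it through.** The plan states no power or precision figure to reproduce: Section 7.6 says the sample size is not based on a power calculation, and Section 7.2 says no hypothesis is tested.

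**1. Which limb of criterion 18 governs.** Washout = max(30 days, 5 × half-life), using the upper limits in Section 1.2.

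- Day 1: 5 × 1 h = 5 h
- 10 mg, Day 28: 5 × 4 h = 20 h
- 15 mg, Day 28: 5 × 9 h = 45 h = 1.9 days

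The half-life limb would bind only if the half-life exceeded 30 × 24 / 5 = 144 h. No half-life is given for 20 mg. On the stated values, 30 days always governs.

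**2. Effect of pre-exposed controls on the Day-1 ratio.** With ten complete pairs, the model in Section 7.1.3 estimates the log ratio as the mean of the ten within-pair log differences. If m controls have Day-1 exposure multiplied by k, the ratio is multiplied by k^(−m/10).

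| Pre-exposed controls | k=1 | k=1.5 | k=2 | k=5 | k=10 |
|---|---|---|---|---|---|
| m=1 | 1.00 | 0.96 | 0.93 | 0.85 | 0.79 |
| m=2 | 1.00 | 0.92 | 0.87 | 0.72 | 0.63 |

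A pre-exposed member of Group 1 would move the ratio the other way: 1.07 at k=2 and 1.26 at k=10 for one subject.

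**3. What the documents say about k.** They give no data after dosing stops and no AOC3 turnover time. If blockade decays with an assumed turnover half-life T in days, the fraction left after 30 days is 0.5^(30/T): 0.1% for T=3, 5% for T=7, 23% for T=14 and 50% for T=30. These are fractions of blockade. Nothing in the documents converts them into k.

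**4. The two pre-dose restrictions.** Section 4.2.2.1 describes BI 1467335 as an irreversible MAO-B inhibitor in vitro and lists MAO inhibitors among drugs prohibited for 5 weeks (35 days) before BI 1467335 dosing. Criterion 18 would admit someone who took BI 1467335 itself 31 days earlier. The two passages do not say how they relate.

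**The case against.** The strongest reply is that the case is unlikely to arise. Sections 3.1 and 4.1.4 admit a control only after the matched impaired subject has completed the study or the treatment period. That adds at least 28 days of treatment, or a wait until the end-of-trial visit on Days 38 to 41, to the unstated time between the 28-day study and this trial's first dose. The real gap for a former volunteer serving as a control is probably well beyond 30 days.

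The known pool is also small: 9 subjects on active drug at 10 mg and 5 completers on active drug at 15 mg (Section 2.3), plus unstated numbers at 20 mg and in the 14-day study. A former volunteer would have to match a particular impaired subject on gender, race, smoking status, age and BMI. Nothing shows that the earlier trials used this site. Criterion 28 and local regulation could also exclude such a person. All of this stands and lowers the likelihood, although none of it requires exclusion.

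The mechanism is hedged too. The protocol says only that accumulation may in part be due to irreversible binding. It does not say that occupancy weeks after stopping raises first-dose exposure, and the unknown residual effect period is invoked to assign adverse events, not to set a washout.

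A reader might take the 58-fold and 159-fold rises in AUC0-24 at 10 mg (Days 14 and 28) as a guide to k. Full 159-fold carry-over in one control would give 159^(−1/10) = 0.60. The documents do not support that: the rises describe uninterrupted daily dosing, and Section 1.2 warns that Day-1 AUC may be underestimated, which would inflate them.

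**Conclusion.** The gap in the eligibility wording is real and its consequence is uncertain. For BI 1467335 the rule reduces to 30 days, and the documents do not show that 30 days restores the state a first-dose endpoint presupposes. For one pre-exposed control in ten, the Day-1 ratio would be multiplied by between 1.00 (no carry-over) and 0.79 (k=10, an assumed value). No value of k, 1 included, can be excluded or favoured from the documents.

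A reader might infer that a renal effect would be hidden. That goes too far. The Day-28 AUC and Cmax are also primary, Section 3.2 treats the multiple-dose data as the clinically relevant ones and expects conditions close to steady state after 28 doses, and the trial only estimates. Nor do the documents say that any former participant would be enrolled. What they support is that Day-1 results could be affected, not that they will be. The priority is minor, and the change is worth making because it costs so little.

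**What to change.** Add one exclusion to Section 3.3.3 for all subjects: previous administration of BI 1467335 (PXS-4728A) in any trial. Keep criterion 18 for other investigational agents. The cost is one eligibility line and one screening question, and a few former volunteers become ineligible. Sample size, model and procedures are unchanged.

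If a full exclusion is thought too strict, the minimum is to record prior BI 1467335 exposure and its last dosing date at screening. The SAP should then prespecify a sensitivity analysis of Day-1 AUC0-24 and Cmax that drops any pair with a pre-exposed member. The cost is one data item and one extra model fit for each Day-1 endpoint. Each dropped pair loses one of the 10 − 1 = 9 error degrees of freedom in that analysis.

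In either case, the protocol should reconcile the 30 days of criterion 18 with the 5-week pre-dose restriction on MAO inhibitors in Section 4.2.2.1, and state which applies to earlier BI 1467335 exposure. That choice is for the sponsor and the investigator.

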### **3.3.4 Removal of subjects from therapy or assessments**

#### **3.3.4.1 Removal of individual subjects**

An individual subject is to be removed from the trial if:

1. The subject withdraws consent for trial treatment or trial participation, without the need to justify the decision
2. The subject needs to take concomitant drugs that interfere with the investigational product or other trial medication
3. The subject is no longer able to participate for other medical reasons (such as pregnancy, surgery, adverse events, or diseases)
4. The subject shows an elevation of AST and/or ALT  $\geq 3$ -fold ULN combined with an elevation of total bilirubin  $\geq 2$ -fold ULN (measured in the same blood sample) and/or needs to be followed up according to the 'DILI checklist' provided in the ISF.

A subject can also be removed from the trial if eligibility criteria are being violated or if the subject fails to comply with the protocol (for instance, by non-adherence to dietary rules, or non-attendance at study assessments).

If a subject is removed from or withdraws from the trial prior to first administration of trial medication, the data of this subject will not be entered in the case report form (CRF) or trial database and will not be reported in the clinical trial report (CTR). If a subject is removed from or withdraws from the trial after first administration of trial medication, this will be documented and the reason for discontinuation must be recorded in the CRF. In this case, the data will be included in the CRF/trial database and will be reported in the CTR. At the time of discontinuation a complete end of trial examination will be performed if possible and the information will be recorded in the CRFs. If the discontinuation occurs before the end of the REP (see [Section 5.2.2.2](#)), the discontinued subject should if possible be questioned for AEs and concomitant therapies at or after the end of the REP in order to ascertain collection of AEs and concomitant therapies throughout the REP, if not contrary to any consent withdrawal of the subject. These discontinuations will be discussed in the CTR.

If it is known that a subject becomes pregnant during the trial, administration of the trial medication has to be stopped immediately, and the subject has to be removed from the trial. The subject is to be followed until she has given birth or until the end of pregnancy. The subject's data are to be collected until the end of the trial (last visit of last subject) and reported in the clinical trial report. For reporting of pregnancy and events refer to [Section 5.2.2.2](#).

